9.5.4. Endpoints

9.5.4.1. Primary Endpoint

The primary endpoint of this investigation is the **incidence of RGn550's ADEs** throughout the investigation.

9.5.4.2. Secondary Endpoints

The secondary endpoints are:

- The **incidence of RGn550's ADEs per severity** throughout the investigation:
 - Incidence of mild ADEs
 - Incidence of moderate ADEs
 - Incidence of severe ADEs
- The **incidence of RGn550's AEs** throughout the investigation
- The **incidence of RGn550's DDs** throughout the investigation.
- The evolution, before and after treatment session at D0 and D7 and then at D52, of:
 - **Automated oculomotor and oculopostural functions**, as assessed through:
 - Convergence, evaluated with the measure of the Near Point of Convergence (NPC)
 - Deviations, evaluated with the cover test and Maddox rod test
 - **Balance function**, as assessed through the following static stabilometric parameters:
 - Statokinesigram area
 - Left/right distribution
- The evolution, before treatment session at D0 and after treatment session at D7 of **executive function**, as assessed with the TMT A&B
- The evolution of **concussion syndrome symptoms** as assessed by the patient with the SCAT5 symptom evaluation tool at D0 before treatment, D7 before treatment, D14 and D52
- The evolution from D0 before treatment to D52 of the concentration of the following **blood markers**:
 - Anti-inflammatory cytokines InterLeukin (IL)-1 receptor antagonist, IL-4, IL-6, IL-10, IL-11 and IL-13
 - S100 calcium binding protein B (S100B)
 - Glial Fibrillary Acidic Protein (GFAP)
 - Ubiquitin C-terminal Hydrolase-L1 (UCH-L1).

These secondary endpoints have been chosen since:

- Convergence insufficiency is an emerging oculomotor-related outcome after a sport-related concussion [26] and the NPC is one of the primary diagnostic tests used to assess convergence insufficiency. Of note, convergence insufficiency rate following concussion was reported to range from 42% to 55% [7].
- The cover and Maddox rod tests are recognized tests to assess ocular deviations [27, 28]. In particular, the Maddox rod test has been used for more than a century in ophthalmology [28].
- Stabilometry is an objective and reproducible method for the recording and evaluation of balance function, in particular following neurologic impairment [29]. Of note, the statokinesigram area is chosen as it is a parameter that might evolve with concussion evolution [30] while the left/right distribution is added as an exploratory parameter.
- The TMT A&B is a recognized test to evaluate executive function [31]. Of note, in the pilot clinical investigation on RGn530 in AD, the TMT B completion time decreased from baseline to W8 in RGn530 group while it increased in the sham group.

| | | |
|--------|---|---|
| RGnCON | Clinical Investigation Plan Version 2.0 - 11 August 2022 |  |
|--------|---|---|

- The SCAT5 is a standardized tool for evaluating concussions designed for use by physicians and licensed healthcare professionals [32].
- Anti-inflammatory cytokines, whose major ones are IL-1, IL-4, IL-6, IL-10, IL-11 and IL-13 [33], are released as part of the neuroimmune response to concussion [34].
- S100B, GFAP and UCH-L1 are regarded as biomarkers of acute brain injury [35].

9.5.5. Description of Visits, Procedures and Data to Collect

Data will be collected at D0, D7, D14 and D52.

The principal investigator will perform the informed consent process, apply treatment and conduct all evaluations apart from the oculomotor/oculopostural and stabilometric tests that will be conducted by the coinvestigator.

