9.2.3. Justification of the Clinical Investigation Design

RGnCON is a prospective, comparative, randomized, simple-blinded, monocentric, pilot clinical investigation:

- A **prospective** design has been chosen since no data on the use of RGn550 in sportspeople suffering from acute concussion syndrome were previously collected.
- This investigation is **comparative**. It involves two parallel groups differing in terms of treatment frequency: half of the patients will be treated with 5 Hz, the other half with 10 Hz. This will allow to determine which frequency is optimal for the patient both in terms of safety and performance.
- Patients will be assigned to one of these two groups through **randomization** (1:1 ratio).
- Patients will not be aware of the group they were assigned to (**simple blinded**).
- A **monocentric** design has been chosen because RGnCON is a pilot investigation.

Various methodological aspects will prevent investigation bias:

- The presence of two groups will allow to take into consideration all confounding factors, apart from placebo effect.
- The unpredictable randomization will spread all known and unknown confounding factors (apart from placebo effect) within the two groups, resulting in comparable groups, and will prevent selection bias.

- Patients will be stratified based on gender (male/female) and concussion history (history/no history of concussion within 6 months prior to inclusion) as such parameters are known to influence current concussion symptoms and complications.
- The analysis will be performed in the Full Analysis Set (FAS) population without methods to replace missing data. However, some of the used models take into consideration missing data.

Of note, the following bias will remain present:

- The follow-up bias and evaluation bias since investigators will not be blinded
- The site effect since only one site will be recruited.

Nevertheless, the primary purpose of this investigation is to evaluate, for the first time, the safety of RGn550 in sportspeople suffering from acute concussion syndrome and explore its performance in this population. In case this investigation demonstrates RGn550's safety in this population, further investigation(s), using a double-blinding design versus sham, and involving more sites, will be conducted to demonstrate RGn550's safety and performance.

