9.5. Clinical Investigation Design

9.5.1. Investigational Medical Devices

Two RGn550 devices producing a 5 Hz frequency and two producing a 10 Hz frequency will be provided by REGEnLIFE to the investigational site. Provided devices will be tracked, during and after the investigation, with assigned serial numbers.

The principal investigator will be trained in the use of RGn550 by REGEnLIFE before the inclusion of the first patient.

Each patient will be treated with the same device throughout the investigation. For a given patient, the other device of the same type (5 Hz or 10 Hz) may only be used in case of malfunction of the initial device.

To maintain simple blinding, the devices will be visually identified as follows:

- The RGn550 devices producing a 5 Hz frequency will be labeled as: Device A1 and Device A2
- The RGn550 device producing a 10 Hz frequency will be labeled as: Device B1 and Device B2.

To track the use of the devices, the principal investigator will mention in the electronic Case Report Form (eCRF) which RGn550 device was used at each treatment session of each patient. In parallel, he will fulfil a treatment sheet associated with the device in question and write down the number of the treated patient, date of treatment, number of treatment session and duration of treatment.

The maximal overall exposure of patients to RGn550 will be of 1 week, since the second, and last, treatment session is planned at Day 7. Exposure during a treatment session will be of 20 min.

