9.5.3. Conduct

9.5.3.1. Patient Inclusion

It is planned to include 50 patients in this investigation (refer to section 9.6.1 for sample size justification).

Based on this number and considering that the site estimated that it would be able to include approximately 3 patients per week, a 4-month inclusion period is planned: from September 2022 to December 2022.

The recruited site will be the Hôpital européen Georges-Pompidou located in Paris. The principal investigator will be a neurologist specialized in sport concussions and the coinvestigator will be a sport physician and posturologist.

In current clinical practice, following a shock, a sportsperson with obvious signs of concussion is examined by a physician within 72 hours after the shock to establish the diagnosis of concussion. For example, in the context of professional rugby, the French federation's regulation requires to follow HIA protocol immediately after the shock and the appearance of such signs. This protocol, composed of three steps, is performed by a physician within 48 hours after the shock:

- Step 1: Assessment during the match using HIA1
- Step 2: Post-match assessment, the same day, using HIA2
- Step 3: 36-48 hours post-injury assessment using HIA3.

The subjects of RGnCON investigation will be identified among sportspersons examined by the principal investigator within 72 hours after the shock. They will be included if they meet eligibility criteria and agree to participate in the investigation. Of note, HIA3 is mentioned in the eligibility criteria as the diagnostic tool for concussion. Indeed, as the principal investigator is the referring neurologist for a lot of rugby clubs and several sports federations, it is expected that most subjects will be professional rugby players for whom this protocol is implemented in current clinical practice. Nevertheless, subjects practicing other sports may be included as well if they have a diagnosis of concussion confirmed by the HIA3, meet the eligibility criteria and agree to participate.

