9.5.3.2. Visits

Three onsite visits will be performed at the following timepoints:

- Day 0 (D0): Inclusion, randomization (to the 5 Hz or 10Hz treatment group) and first treatment session
- Day 7 (D7): Second treatment session
- Day 52 (D52): Evaluation 45 days after the last treatment session.

In addition, at Day 14 (D14), the patient will be asked to remotely assess his/her concussion syndrome symptoms.

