9.5.5.1. Inclusion, Randomization and First Treatment Session Visit (D0)

During this visit, the principal investigator will **offer patients who meets eligibility criteria to participate in the investigation**. In particular, to be included, patients must have a diagnosis of concussion confirmed via the HIA3 tool. This tool is the third, and last, stage of the head injury assessment protocol. It is to be performed after two night's rest (36-48 hours post-head impact event) to further assess clinical progress and identify a late diagnosis of concussion [36]. The French version of this tool, presented in Appendix 12.1 [36], will be used during this investigation.

Of note, women of childbearing potential will undergo a **pregnancy test** to ensure they are not pregnant and thereby meet the corresponding eligibility criteria.

The principal investigator will thus **inform the patients and obtain their consent** as described in section 9.12.

The investigators will then **collect the following data**:

- **Eligibility criteria**
- **Demographic and clinical data**

Data such as gender, age, sport practiced, concussion history and concomitant treatments will be collected, along with parameters that are known to influence oculomotor/oculopostural or stabilometric tests such as:

- For oculomotor/oculopostural tests:
 - Regular orthoptic rehabilitation sessions
- For stabilometric test:
 - Surgery of the lower limbs within 6 months prior to inclusion.

The investigators will also **perform the following tests**:

- **NPC**

The NPC is the closest point in space where the patient's eyes can converge [7, 26].

An objective measurement of the NPC will be performed in line with previous literature. The measurement will be conducted with a fixation stick placed at 30-40 cm of the patient's eye within the median plan. The patient will keep its glasses on in case he/she has glasses. The patient will be asked to "focus on the object with both eyes". The object will then be moved by the investigator closer to the patient's eyes until the patient sees two distinct images or until the investigator observes an outward deviation of one eye. The distance from this point to the lateral canthus will then be measured using a ruler [26].

The measure will be performed three consecutive times and the mean of these three measurements will be calculated.

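### The coinvestigator grades the cover test by eye and can set the NPC stopping point but is left unblinded, although another physician treats; the 5 Hz versus 10 Hz comparison of these two secondary tests carries an avoidable risk of rater bias

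*Protocol*

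**What the plan says.** **Roles.** Under Protocol 9.5.5 the principal investigator takes consent, treats, and is to "conduct all evaluations apart from the oculomotor/oculopostural and stabilometric tests that will be conducted by the coinvestigator". Protocol 9.5.3.1 makes the principal investigator a neurologist, while "the coinvestigator will be a sport physician and posturologist". The person who treats and the person who rates are therefore different. Device logging also lies with the first: "the principal investigator will mention in the electronic Case Report Form (eCRF) which RGn550 device was used at each treatment session of each patient" (Protocol 9.5.1).

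**Blinding.** Protocol 9.5.5.1 and 9.7 limit blinding to patients. Protocol 9.2.3 lists among the biases that remain: "The follow-up bias and evaluation bias since investigators will not be blinded". Protocol 9.5.1 prints the device key: "The RGn550 devices producing a 5 Hz frequency will be labeled as: Device A1 and Device A2", with B1 and B2 for 10 Hz.

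**Tests.** In Protocol 9.5.5.1 the coinvestigator grades the cover test in four qualitative categories (0 to 3), one eye at a time. An NPC reading ends when the patient reports double vision "or until the investigator observes an outward deviation of one eye". The distance is then measured by ruler and averaged over three readings.

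**Use of the results.** On the two-group comparison, Protocol 9.2.3 says: "This will allow to determine which frequency is optimal for the patient both in terms of safety and performance". SAP 6.2.2 reduces the cover test to normal in both eyes versus abnormal in at least one. SAP 8.5.1.1 fits mixed models with group, period and their interaction. Its example template for categorical endpoints shows 10 Hz versus 5 Hz odds ratios by visit.

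**The concern.** The treating physician has to know which device is in use. Nothing in either document says that the rater has to. The roles are already divided and the devices already carry code labels, so the coinvestigator could be kept unaware of the frequency without a sham, extra staff or extra visits. The plan describes no such step.

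What is at stake is the choice of frequency. If the rater grades borderline eye movements differently by arm, the error goes into the between-frequency estimate that Protocol 9.2.3 proposes to use. The line between normal fixation and a light restitution movement is a visual judgement, and after the SAP's dichotomy it decides the patient's category. A larger later study run at the chosen frequency would not correct a wrong choice.

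**Working it through.** **1. The plan's own figure.** Protocol 9.6.1 gives 0.87 as the probability of at least one ADE with 50 patients and an ADE probability of 0.04. Check: 1 − 0.96^50 = 0.8701. It reproduces, and it does not depend on who rates the eye tests.

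**2. Which tests are exposed** (Protocol 9.5.5 and 9.5.5.1):

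| Test | What produces the value | Exposure to this rater |
|---|---|---|
| Cover test | Coinvestigator's visual grade | Highest |
| NPC | Ruler distance, mean of three; end point reported by the patient or seen by the examiner | Lower |
| Maddox rod | Patient says where the line lies; prism value | Lower still |
| Stabilometry | Platform sensors | Lower still |

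The Trail Making Test (TMT) is given by the unblinded principal investigator. It is outside this point.

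**3. Which time points are exposed.** Protocol 9.5.5.1 describes the D0 pre-treatment tests, then the SCAT5, blood sample and randomisation, then treatment. In that order the D0 pre-treatment ratings cannot reflect allocation. The ratings at D0 after treatment, D7 before, D7 after and D52 can. With a clean baseline, a later shift passes into the change from baseline.

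**4. Illustration of size for the cover test.** The documents give no misgrading rate and no abnormal share for this test, so both are assumed.

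- n = 25 per arm (50 patients, 1:1); one visit; no true difference.
- True abnormal share p = 0.30, 0.50 or 0.70 in both arms.
- In one arm only, a share m = 0.20 of truly abnormal patients is graded normal.
- Observed share in that arm: q = p(1 − m). False difference: p − q. Expected misgraded patients: 25pm.
- Marginal odds ratio: [q/(1 − q)] / [p/(1 − p)].
- 95% half-width: 1.96 × √[p(1 − p)/25 + q(1 − q)/25].
- Rejection rates: exact enumeration of the two binomials, two-sided 0.05.

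| p | q | Misgraded patients | False difference | Odds ratio | Half-width | Pooled z (no bias) | Fisher (no bias) |
|---|---|---|---|---|---|---|---|
| 0.30 | 0.24 | 1.5 | 0.06 | 0.74 | 0.246 | 0.081 (0.054) | 0.037 (0.023) |
| 0.50 | 0.40 | 2.5 | 0.10 | 0.67 | 0.274 | 0.131 (0.065) | 0.078 (0.033) |
| 0.70 | 0.56 | 3.5 | 0.14 | 0.55 | 0.265 | 0.193 (0.054) | 0.119 (0.023) |

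One misgraded patient moves an arm by 1/25 = 4 points. With m = 0.10 the false difference is 3 to 7 points; with m = 0.30 it is 9 to 21 points.

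**5. Effect of testing two eyes.** The 20% above is a patient-level rate. A patient abnormal in both eyes becomes normal only if both eyes are misgraded. Assume a 20% error per eye, independent between eyes, and half of abnormal patients affected in both eyes. The patient-level rate is then 0.5 × 0.20 + 0.5 × 0.20² = 0.12, and the false difference is 0.12p = 0.036, 0.060 or 0.084, about 4, 6 or 8 points. The opposite error, normal graded abnormal, needs only one eye and is not modelled.

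These are not error rates of the planned mixed logistic model. No figure is offered for NPC.

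**The case against.** **It is disclosed, and the study is a pilot.** Protocol 9.2.3 names evaluation bias, puts first safety evaluation first, and leaves double-blinding against sham to later work. This stands as far as it goes: the bias is not hidden and the endpoints are secondary. But deferring a sham comparison gives no reason to leave a separate rater aware of 5 versus 10 Hz.

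**There is no evident favourite.** Both arms are active and no expected winner is stated. A rater who simply hopes the device works would inflate both arms alike. This also stands. It is why no direction or size can be given, and why blinding to frequency would not remove expectation bias in before/after change.

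**The illustration is generous.** Step 5 of the check shows this is fair, and the modelled bias lies within sampling error.

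**A stronger reading that fails.** A reader might infer that baseline ratings are exposed too, because the schedule table puts the randomisation row above the tests and Protocol 9.5.3.2 runs the steps together: "Day 0 (D0): Inclusion, randomization (to the 5 Hz or 10Hz treatment group) and first treatment session". The documents do not support this. The narrative in 9.5.5.1 puts randomisation after the D0 tests. The table rows are not chronological: the treatment row sits below tests that are repeated after treatment. The 9.5.3.2 line is a visit summary.

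**Conclusion.** The point holds in a limited form. A rater who does not treat is left unblinded without a stated reason. One secondary test graded by eye, and to a lesser extent NPC, are exposed in the between-frequency comparison after randomisation. On the assumed figures, a one-arm patient-level misgrading of 20% shifts the cover test difference by 6 to 14 points, and by about 4 to 8 points under the two-eye assumption in the check. Either is smaller than the half-width of about 25 to 27 points. Such a bias could tilt an estimate used to choose a frequency; it would seldom create significance by itself.

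A reader might infer that the frequency comparison is biased, or that the trial's error rate is inflated by a known amount. Neither follows: the misgrading is assumed, and actual bias has not been shown. The primary ADE proportion and the sample size are untouched. This is a worthwhile, inexpensive improvement with medium confidence, and it does not threaten the study's main purpose.

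**What to change.** **If any assessments remain:**

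1. In Protocol 9.5.5 and 9.7, state that the coinvestigator is blind to allocation: no eCRF access to the randomisation system, device field or treatment sheets; absent during set-up and treatment; not told the device label (A or B) or its key. Withholding the label matters as well as the key, because labels are fixed by arm and would let a rater group patients.
2. In 9.5.5.1, state outright that randomisation follows the D0 pre-treatment tests, as the narrative there already describes. The schedule row need not move.
3. In 9.2.3, limit the remaining evaluation bias to before/after change, TMT and ADE causality.

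**If assessments are complete**, which the planned last visit of February 2023 (Protocol 9.17) and the data review of July 2023 (SAP 8.5.1.1) suggest: report whether the coinvestigator knew the allocation, and qualify the between-frequency cover test and NPC results accordingly.

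**Cost.** An eCRF role restriction and protocol wording, with no added staff, visits or procedures. The downside is that the coinvestigator cannot stand in for treatment or device-related recording in patients he or she assesses. After data collection, the only cost is a reporting statement.

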9.5.5.1. Inclusion, Randomization and First Treatment Session Visit (D0)

During this visit, the principal investigator will **offer patients who meets eligibility criteria to participate in the investigation**. In particular, to be included, patients must have a diagnosis of concussion confirmed via the HIA3 tool. This tool is the third, and last, stage of the head injury assessment protocol. It is to be performed after two night's rest (36-48 hours post-head impact event) to further assess clinical progress and identify a late diagnosis of concussion [36]. The French version of this tool, presented in Appendix 12.1 [36], will be used during this investigation.

Of note, women of childbearing potential will undergo a **pregnancy test** to ensure they are not pregnant and thereby meet the corresponding eligibility criteria.

The principal investigator will thus **inform the patients and obtain their consent** as described in section 9.12.

The investigators will then **collect the following data**:

- **Eligibility criteria**
- **Demographic and clinical data**

Data such as gender, age, sport practiced, concussion history and concomitant treatments will be collected, along with parameters that are known to influence oculomotor/oculopostural or stabilometric tests such as:

- For oculomotor/oculopostural tests:
 - Regular orthoptic rehabilitation sessions
- For stabilometric test:
 - Surgery of the lower limbs within 6 months prior to inclusion.

The investigators will also **perform the following tests**:

- **NPC**

The NPC is the closest point in space where the patient's eyes can converge [7, 26].

An objective measurement of the NPC will be performed in line with previous literature. The measurement will be conducted with a fixation stick placed at 30-40 cm of the patient's eye within the median plan. The patient will keep its glasses on in case he/she has glasses. The patient will be asked to "focus on the object with both eyes". The object will then be moved by the investigator closer to the patient's eyes until the patient sees two distinct images or until the investigator observes an outward deviation of one eye. The distance from this point to the lateral canthus will then be measured using a ruler [26].

The measure will be performed three consecutive times and the mean of these three measurements will be calculated.

In accordance with previous literature, a NPC \leq 5 cm will be considered normal while a NPC $>$ 5 cm will be considered abnormal [37].

- **Cover test**

There are different variants of the cover test. The unilateral cover test will be used, which consists into covering one eye, horizontally moving a target 5 cm in front of the non-covered eye, and then uncovering the covered eye and observing its movements. If it moves to regain fixation, the patient exhibits deviation. If the covered eye moves to recover fixation (restitution movement), the test is positive. The patient will keep its glasses on in case he/she has glasses.

The result will be measured qualitatively by the co-investigator using the following four categories:

- Normal fixation = 0
- Light restitution movement = 1
- Important restitution movement = 2
- Deviated eye without restitution movement = 3.

The test will then be repeated on the other eye.

- **Maddox Rod test**

This test will be performed with a pen torch and a red Maddox rod consisting of 17 biconvex cylinders that have enough convergence to transform the image of a white light point into a red line perpendicular to the cylinder axis [28]. During this test, the patient will keep its glasses on in case he/she has glasses.

The Maddox rod will be placed in front of one eye with the cylinders first oriented horizontally. The fixed light point will be placed at least 3 meters from the patient, at the height of his/her eyes, and will be focused on the midline of the patient's face. The patient will indicate where the vertical red line is positioned relative to the white point. If the white light and vertical red line are not overlapping, there is a horizontal deviation (see Figure 8). In case a deviation is identified, prisms will be held in front of the Maddox rod until the line is centered on the light. The value of the prism will quantify the deviation [38]. The horizontal deviation will be measured on one eye only.

Then, the Maddox rod will be placed in front of the same eye with the cylinders oriented vertically. If the white light and vertical red streak are not overlapping, there is a vertical deviation (see Figure 9). Similarly, in case of deviation, prisms will be used to quantify it [38]. The test will then be repeated on the other eye to measure the vertical deviation of the other eye.

[figure not shown]

Figure 8: Horizontal orientation of the Maddox rod to identify horizontal deviation (BI: Base In, BO: Base Out) [38]

[figure not shown]

Figure 9: Vertical orientation of the Maddox rod to identify vertical deviation (BD: Base Down, BU: Base Up, LH: Left Hyperphoria, Rh: Right hypophoria, RH: Right Hyperphoria) [38]

- **Static stabilometric test**

Static stabilometric parameters are measured with the use of a stabilometric platform equipped with sensors that monitor the evolution in time of the patient's center of pressure and its movements relative to the center of the platform. The signal is digitalized, evaluated by special computer program and results are visualized on the monitor and recorded [29].

The patient will be asked to stand on KFORCE Plates (a stabilometric platform manufactured by KINVENT HELLAS, see Figure 10) either barefoot or with his/her shoes and orthopedic inserts in case the patient has inserts. A 30 s-record will be performed, two times consecutively: one time with the patient's eyes open and one time with the patients' eyes closed.

Following these two records, the two values of the following parameters will be collected, and their mean will be calculated:

- The statokinesigram area

The statokinesigram is the projection onto a 2-dimensional space of the trajectory of the patient's center of pressure [39]. Its area is measured in mm². The larger the area is, the higher the patient's imbalance is.

- The left/right distribution

The left/right distribution comprises two percentages representing the patient's body weight distribution on his/her left versus right foot. If 50% is obtained for each foot, the patient is stable.

Figure 10: Picture of KFORCE Plates

- **TMT A&B**

The TMT is an executive function test reflecting various cognitive processes such as selective attention, motor activity and flexibility. In Part A, the subject is instructed to trace a line that connects circled numbers in consecutive order (see Appendix 12.2.1). In Part B, the subject is asked to trace a line that connects circled numbers and circled letters in consecutive order while alternating between numbers and letters (see Appendix 12.2.2). The time to perform the task, number of correct moves and number of errors are collected [31].

Following this, the patient will evaluate his/her symptoms using the **SCAT5 symptom evaluation tool**. The patient will rate the intensity of every symptom from 0 (none) to 6 (severe) using a form. This will allow to calculate the total number of symptoms (out of 22) and the symptom severity score (out of 132) (see Appendix 12.3).

A **blood sample** will also be obtained from the patients by a nurse. The blood sample analysis will be performed by Montpellier Neuroscience Institute (*Institut de Neuroscience de Montpellier*) following the institute standard practice.

During the visit, the patients will be **randomized** in a 1:1 ratio to the 5 Hz group or 10 Hz group using the centralized Interactive Web Response System (IWRS) incorporated into the eCRF. A block randomization method will be used. Only patients will be blinded to their assigned treatment.

Depending on their assigned group, the patients will then be **treated** with one of the 5 Hz RGn550 devices or one of the 10 Hz RGn550 devices for 20 min. To perform the treatment, the principal investigator will follow the below instructions:

- Make the patient comfortable.
- Install the helmet on the patient's head, taking care not to bump it with the modules.
- Lightly tighten the soft helmet holding wire and check the positions of the modules. Each module can be moved slightly to adjust its position.
- On the control unit, in the menu on the left, choose the option 'Program' and choose the proposed treatment
- Finally press the red arrow to start the treatment.

A countdown is displayed on the screen indicating the time remaining until the end of the treatment session. At each treatment session, the principal investigator will fulfil a treatment sheet associated with the used device and mention the number of the treated patient, date of treatment, number of

treatment session and duration of treatment. To stop the treatment, the principal investigator will press the red button with a cross inside that is displayed on the screen (a confirmation message will be displayed to avoid any manipulation error).

Following treatment, the investigators will:

- **Perform the following tests** following the methodology described above:
 - NPC
 - Cover test
 - Maddox rod test
 - Static stabilometric test
- **Collect any AEs and DDs** that occurred during the visit.

